7.2.2.1 Demographics

The following demographic variables will be summarized and presented for each treatment group. This analysis is also conducted by Study Region and Protocol Version Number (used for confirmation of the Inclusion criteria and the Exclusion criteria), but will not conduct to explore imbalance between treatment groups.

Table 5. Demographic Variables and Analysis Methods

Item	Classification	Testing Method
Age (at the time of Informed Consent)	Measurement value	one-way ANOVA
	<65, >= 65	-
Sex	Male, Female	chi-squared test
Height[Screening] (cm)	Measurement value	one-way ANOVA
Body Weight[Screening] (kg)	Measurement value	one-way ANOVA
	<- 40 kg, 40 kg <- 60 kg, 60 kg <- 80 kg, > 80 kg	-
BMI [Screening] (kg/m2)	Measurement value	one-way ANOVA
Complications	No, Yes	-
Previous Medications	No, Yes	-
Concomitant Medications	No, Yes	-
Concomitant DMARD at Baseline	No, Yes	chi-squared test
Concomitant MTX at Baseline	No, Yes	chi-squared test
Concomitant DMARD at Baseline category	MTX, DMARD except for MTX only, None	chi-squared test
Concomitant Steroid at Baseline	No, Yes	chi-squared test
Prednisone dose at Baseline (mg/day)	Measurement value	one-way ANOVA
	None, 0 <- 5 mg/day, > 5 mg/day	-
Study Region	Japan, Korea, Taiwan	chi-squared test
Protocol Version Number (used for confirmation of the Inclusion criteria and the Exclusion criteria)	<= Version 2.0, >= Version 3.0	chi-squared test

7.2.2.2 Baseline Disease Activity

The following baseline disease activity variables will be summarized by descriptive statistics, and imbalance between treatment groups (except for reference group) will be considered based on a one-way ANOVA model with fixed effect for treatment group. This analysis is also conducted by Study Region and Protocol Version Number (used for confirmation of the Inclusion criteria and the Exclusion criteria), but will not conduct to explore imbalance between treatment groups.

- TJC-68
- TJC-28
- SJC-66
- SJC-28
- SGAP (100 mm VAS)
- SGA (100 mm VAS)
- PGA (100 mm VAS)
- HAQ-DI (scale 0 - 3)
- CRP (mg/dL)

- ESR (mm/hr)
- DAS28-CRP
- DAS28-ESR
- SDAI score
- CDAI score
- WPAI
- SF-36V2®

In addition, following baseline efficacy categorical variables will be summarized as well.

- Baseline CRP (< 1.0, >= 1.0)
- Baseline DAS28-CRP (<= 3.2, 3.2<-5.1, > 5.1)
- Baseline DAS28-ESR (<= 3.2, 3.2<-5.1, > 5.1)

7.2.2.3 RA History

The following RA history variables will be summarized and presented for each treatment group and imbalance between treatment groups (except for reference group) will be tested. This analysis is also conducted by Study Region and Protocol Version Number (used for confirmation of the Inclusion criteria and the Exclusion criteria), but will not conduct to explore imbalance between treatment groups.

Table 6. RA History and Analysis Methods

Item		Classification	Testing Method
ACR 1991 Revised Criteria for Global Functional Status in RA		Class I, Class II, Class III	chi-squared test
Steinbrocker Classification		Stage I, Stage II, Stage III, Stage IV	chi-squared test
Prior Surgical Procedure to Treat RA		No, Yes	chi-squared test
Duration of RA (years)		Measurement value	one-way ANOVA
		< 5 years, >- 5 years	-
		< 1 year, 1 year -<5 years, 5 years -< 10 years, >- 10 years	-
Onset Age of RA (years), calculated as: (onset date of RA – date of birth+1) / 365.25		-	one-way ANOVA
Prior MTX	Use	Non-User, User	chi-squared test
	Maximum Dose (mg/week)	Measurement value	-

	Reactivity	Response, Inadequate Response, Unknown	-
	Tolerance	Intolerance, Tolerance, Unknown	-
MTX Dose at Baseline (mg/week)		Measurement value	one-way ANOVA
		None, 0 <- 8 mg/week, 8 <- 12 mg/week, > 12 mg/week	
Prior Non-Biologic DMARD Except for MTX	Use	Non-User, User	chi-squared test
Prior Anti-TNF DMARD Use	Use	Non-User, User	chi-squared test
Prior Biologic DMARD	Use	Non-User, User	chi-squared test
	Reactivity	Response, Inadequate Response, Unknown	-
Prior Biologic DMARD-IR		No, Yes	chi-squared test
Number of Prior Biologic DMARDs		0, 1, 2, >= 3	chi-squared test
Number of Prior DMARDs (including biologics)		0, 1, 2, >= 3	chi-squared test
Prior Adalimumab	Use	Non-User, User	-
	Reactivity	Response, Inadequate Response, Unknown	-
	Tolerance	Intolerance, Tolerance, Unknown	-
Prior Golimumab	Use	Non-User, User	-
	Reactivity	Response, Inadequate Response, Unknown	-
	Tolerance	Intolerance, Tolerance, Unknown	-
Prior Infliximab	Use	Non-User, User	-
	Reactivity	Response, Inadequate Response, Unknown	-
	Tolerance	Intolerance, Tolerance, Unknown	-
Prior Certolizumab Pegol	Use	Non-User, User	-
	Reactivity	Response, Inadequate Response, Unknown	-
	Tolerance	Intolerance, Tolerance, Unknown	-
Prior Abatacept	Use	Non-User, User	-
	Reactivity	Response, Inadequate	-

		Response, Unknown	
	Tolerance	Intolerance, Tolerance, Unknown	-
Prior Tocilizumab	Use	Non-User, User	-
	Reactivity	Response, Inadequate Response, Unknown	-
	Tolerance	Intolerance, Tolerance, Unknown	-
Prior Rituximab	Use	Non-User, User	-
	Reactivity	Response, Inadequate Response, Unknown	-
	Tolerance	Intolerance, Tolerance, Unknown	-
Prior Denosumab	Use	Non-User, User	-
	Reactivity	Response, Inadequate Response, Unknown	-
	Tolerance	Intolerance, Tolerance, Unknown	-

7.2.2.4 Medical History

Medical history will be coded using MedDRA (Version 11.1) and summarized. All summaries will be provided for SAF. This analysis is also conducted by Study Region and Protocol Version Number (used for confirmation of the Inclusion criteria and the Exclusion criteria).

7.2.3 Previous and Concomitant Medications

Previous DMARD medications up to Screening will be summarized as described in 7.2.2.3.

In addition to this, previous and concomitant medications (Non-Biologic DMARD/ Medications except for Non-Biologic DMARD) will be coded using WHODDE(B2) (V2011SEP) and summarized with preferred WHO name, respectively from following CRF page. Concomitant medications are defined as any drug medications after the first dose of study drug or reference drug up to the last dose date of study drug and before the last efficacy evaluation at Week52 or Withdrawal.

[Concomitant Medication 2B -page of the CRF]

[Concomitant Medication (Non-Biologic DMARD)]

Subjects taking the same medication multiple times will be counted once per medication.

All summaries will be provided for SAF. This analysis is also conducted by Study Region and Protocol Version Number (used for confirmation of the Inclusion criteria and the Exclusion criteria).

7.3 Study Drugs

7.3.1 Exposure

In this section, following analyses will be conducted and these analyses are also conducted by Study Region and Protocol Version Number (used for confirmation of the Inclusion criteria and the Exclusion criteria).

The following information on drug exposure will be presented for each treatment group for the SAF:

- Number and percent of subject with dose suspensions or interruptions by treatment group.

Duration of exposure will be summarized in two ways.

- Descriptive statistics will be presented by treatment group.
- Exposure time up to Week 12 will be categorized according to the following categories by treatment group:
 - 1 -< 29 days
 - 29 -< 57 days
 - 57 -< 85 days
 - 85 days -
- Exposure time for Overall Period will be categorized according to the following categories by treatment group:
 - 1 -< 85 days
 - 85 -< 197 days
 - 197 -< 281 days
 - 281 -< 365 days
 - 365 days -

Counts and percentages of subjects in each of these categories will be summarized for each treatment group for the SAF.

7.3.2 Treatment Compliance

Overall treatment period compliance, treatment compliance during the 12 weeks of study (up to Weeks 12) with the dosing schedule will be examined for subjects in the SAF whose total study drug or reference drug count and first and last days of treatment are known. These analyses will be summarized in two ways for the SAF:

- Descriptive statistics for overall treatment period will be presented by Treatment Sequence Set (including those initially treated as Placebo group or Reference group).

- Descriptive statistics up to Week 12 will be presented by Initial Randomization Set.
- Percent compliance for overall treatment period will be categorized according to the following categories by treatment group:
 - <50%
 - 50% -<75%
 - 75% -<90%
 - 90% - 100% or greater
- Percent compliance up to Week 12 will be categorized according to the following categories by treatment group:
 - <50%
 - 50% -<75%
 - 75% -<90%
 - 90% - 100% or greater

These analyses are also conducted by Study Region and Protocol Version Number (used for confirmation of the Inclusion criteria and the Exclusion criteria).

For Drug Suspension and Interruption, following will be summarized.

- Experience For Drug Suspension
- Experience For Drug Interruption
- The Number of Experience Drug Suspension Per Subject
- The Number of Experience Drug Interruption Per Subject

These analyses are also conducted by Study Region and Protocol Version Number (used for confirmation of the Inclusion criteria and the Exclusion criteria).

7.4 Analysis of Efficacy

Efficacy analysis will be conducted on FAS and PPS. The interpretation of results from statistical tests will be based on the FAS. In the primary analysis, the purpose of using PPS is to assess the robustness of the results from the statistical tests based on FAS.

Efficacy analysis up to Week 12 including primary analysis will be performed by Initial Randomization Set. Efficacy analysis up to Week 52 will be performed by Treatment Sequence Set for secondary purpose. Details for analysis groups will be described in 10.1 Appendix1 and 10.2 Appendix2.

7.4.1 Analysis of Primary Endpoint(s)

Summary for analysis of primary endpoints are displayed at Section 10.1 Appendix 1.

7.4.1.1 Primary Analysis

Primary analysis will be conducted on FAS. For the ACR20 response at Week 12/ET, pairwise comparisons to placebo will be performed at each ASP015K dose level using logistic regression model with treatment group (Placebo, ASP015K 100 mg, and ASP015K 150 mg) as the factor and the prior biologic-DMARD-IR*, concomitant DMARD at Baseline use*, and study region (Japan, Korea, and Taiwan)* as the covariates. For multiplicity adjustment in the primary analysis, following closed testing procedure shown below will be done. Only if quasi-complete separation, or complete separation occurs in the logistic model, then the study region, the prior biologic-DMARD-IR, and concomitant DMARD at Baseline use will be removed from the logistic regression model, one by one, sequentially.

*: The covariate (the prior biologic-DMARD-IR, concomitant DMARD at Baseline use, and study region) will not be included in the logistic regression model when these variables are used as a subgroup factor.

Two null hypotheses will be constructed:

- H_{01} : ACR20-CRP response at Week 12/ET in ASP015K 150 mg is equal to that in placebo
- H_{02} : ACR20-CRP response at Week 12/ET in ASP015K 100 mg is equal to that in placebo

The accompanying alternative hypotheses are:

- H_{11} : ACR20-CRP response at Week 12/ET in ASP015K 150 mg is not equal to that in placebo
- H_{12} : ACR20-CRP response at Week 12/ET in ASP015K 100 mg is not equal to that in placebo

Step 1. ACR20-CRP response at Week 12/ET: ASP015K 150 mg vs. Placebo

Step 2. ACR20-CRP response at Week 12/ET: ASP015K 100 mg vs. Placebo

The null hypotheses at Step 1 will be tested by Wald test at a two-sided significance level of 0.05.

If it is statistically significant, the next step (Step 2) will be initiated and implemented in the same manner. Otherwise, it is completion of the hypothesis test.

For each comparison, only the data for two treatment groups to be compared will be used.

For the missing data imputation of ACR20-CRP at Week 12/ET, Last Observation Carried Forward (LOCF) methodology will be used.

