4 SAMPLE SIZE

One hundred subjects per group will receive the study drug and 200 subjects the reference drug (a total of 500 subjects).

[Rationale for the sample size]

Based on 015K-CL-RAJ1 result and efficacy result from other RA drugs [XELJANZ[®], tablet, 5 mg, CTD (2013)] [CIMZIA, sc, 200 mg, Syringe, CTD (2012)], 62 subjects per group will provide 90% power to detect a difference assumed in the Step 2 in the closed testing procedure (described in Section 7.4.1.1 Primary Analysis) under the following assumptions. In addition, it is assumed that ACR20 response rate of each country (Japan, Korea and Taiwan) is similar.

- ACR20 response rate at Week 12 in the placebo group: 25%
- ACR20 response rate at Week 12 in the ASP015K 100 mg group: 54.5%

- ACR20 response rate at Week 12 in the ASP015K 150 mg group: 65.5%
- Two-sided significance level of 0.05

On the other hand, according to the Extent of Population Exposure to Assess Clinical Safety for Drugs Intended for Long-term Treatment of Non-life-threatening Conditions (PAB/PCD Notification No.592, dated 24 May 1995), ("the long-term treatment guideline"), a sample size of 300-600 subjects under long-term treatment (6 months) is adequate to observe delayed adverse events at a reasonable frequency (generally, 0.5% to 5%) and to observe whether there is an increase in high-frequency adverse events during the later stage of treatment. For treatment lasting 1 year, 100 subjects is acceptable. It is also described in "Guidelines on methodology for clinical assessment of antirheumatic drugs" (PFSB/ELD Notification No. 0217001, dated 17 February 2006) that 100 subjects for 1 year are necessary.

Therefore, to collect data for 300 subjects for 6 month period, and for 100 subjects for 1 year period in both ASP015K 100 mg and 150 mg groups among 015K-CL-RAJ2/RAJ3/RAJ4 studies as long-term treatment data, approximately 80 subjects per treatment group (400 subjects in total) as a target are necessary to be enrolled in Japan. In addition, the target sample size for Taiwan is set at 10 subjects per treatment group (50 subjects in total) as a target in consideration of the requirement of regulatory authority in Taiwan (10% or more Taiwan subjects) and target sample size for Korea is also set at 10 subjects per treatment group (50 subjects in total) as a target. Therefore, the target sample size per treatment group is set at 100 subjects in total for 3 regions.

[Rationale for the sample size for the reference group]

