7.4.2 Analysis of Secondary Endpoints

Refer to Section 10.2 Appendix 2. They includes categorical, continuous, and time-to-event variables, with "X" indicating that the variable will be analyzed. As for secondary variables, no multiplicity adjustment will be done. Basically, analysis of secondary endpoints will be performed by Initial Randomization Set and Treatment Sequence Set defined at Section 7.1.

The secondary variables and analyses are as follows:

<Initial Randomization Set>

- Categorical variables at each visit (including Baseline, Weeks 4, 8, 12, 12/ET) will be analyzed using logistic regression model, as described for the primary efficacy variable, unless otherwise specified in Section 10.2 Appendix 2.
- For continuous variables, raw value and change from baseline variables at each visit (Baseline, Weeks 4, 8, 12, 12/ET) will be analyzed using the ANCOVA model with treatment group (Placebo, ASP015K 100 mg, and ASP015K 150 mg) as the factor, and the prior biologic-DMARD-IR, concomitant DMARD at Baseline use, study region (Japan, Korea, and Taiwan), and baseline value as the covariates. In addition to this, sensitivity analysis to assess the impact of HAQ-DI caused by inappropriate description in the local questionnaire in Taiwan will be conducted similarly as described in 7.4.1.2.
- Time to the first response analysis will be analyzed similarly as described in 7.4.1.5.
 - ACR50-CRP
 - ACR70-CRP
 - DAS28-CRP <2.6
 - SDAI score <= 3.3
 - CDAI score <= 2.8
 - ACR/EULAR score for remissionAs for DAS28-CRP < 2.6, SDAI score <= 3.3, CDAI score <= 2.8, ACR/EULAR score for remission, if the event is occurred at baseline, then that subject is excluded from this analysis.
- Graphical analysis (including Baseline, Weeks 4, 8, 12, 12/ET).

- ACR20/50/70-CRP will be plotted for over time.
- The mean-standard deviation plot of actual values and changes from baseline will be presented for DAS28-CRP and DAS28-ESR.
- To visually explore possible relationships between ACR20-CRP and DAS28-CRP, 2-panel line graphs of DAS28-CRP over time will be plotted for ACR20-CRP responders (in 1 panel) and non-responders (in another panel). Similar graphs will be provided for DAS28-ESR.

<Treatment Sequence Set>

- Categorical variables at each visit (including Baseline, Weeks 4, 8, 12, 16, 20, 24, 28, 32, 36, 40, 44, 48, 52, EOT) will be summarized as described in Section 10.2 Appendix 2.

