10.2 Appendix 2: Overview of Secondary Endpoints

Table 19 summarizes the analyses of the primary and secondary efficacy variables, with "X" indicating that the variable will be analyzed. All analyses will be based on the FAS, unless otherwise specified.

Table 19. Overview of Secondary Endpoints analysis

Analysis Type/Analysis Variable ¹		CRP	ESR	None	Treatment Group	Analysis Method ²
Categorical Variables						
1.1.1.1	Percentage of subjects achieving ACR20/50/70 at each visit (Weeks 4, 8, 12)	X	X		Placebo, 100mg, 150mg, Reference	Logistic regression
1.1.1.2	Percentage of subjects achieving ACR20/50/70 at each visit (Weeks 4, 8, 12) Subgroup Analysis (Study Region, Protocol Version Number)	X			Placebo, 100mg, 150mg, Reference	Logistic regression
1.1.2	Percentage of subjects achieving ACR20/50/70 at each visit (Weeks 4, 8, 12, 16, 20, 24, 28, 32, 36, 40, 44, 48, 52, EOT)	X			100mg, 150mg, Placebo to 100mg at Week 12, Placebo to 150mg at Week 12, Reference	No statistical test
1.2.1	Line graph of 1.1.1	X	X		Placebo, 100mg, 150mg, Reference	No statistical test
1.2.2	Line graph of 1.1.2	X			100mg, 150mg, Placebo to 100mg at Week 12, Placebo to 150mg at Week 12, Reference	No statistical test
2.1	Percentage of subjects achieving ACR20 response at Week 4 and sustaining response at each visit (Weeks 8, 12)	X			Placebo, 100mg, 150mg, Reference	Logistic regression

2.2	Percentage of subjects achieving ACR20 response at Week 8 and sustaining response at Week 12	X			Placebo, 100mg, 150mg, Reference	Logistic regression
3.1	Percentage of subjects achieving DAS28 score < 2.6 at each visit (Baseline, Weeks 4, 8, 12, 12/ET)	X	X		Placebo, 100mg, 150mg, Reference	Logistic regression
3.2	Percentage of subjects achieving DAS28 score < 2.6 at each visit (Baseline, Weeks 4, 8, 12, 16, 20, 24, 28, 32, 36, 40, 44, 48, 52, EOT)	X	X		100mg, 150mg, Placebo to 100mg at Week 12, Placebo to 150mg at Week 12, Reference	No statistical test
3.3	Percentage of subjects achieving DAS28 score <= 3.2 at each visit (Baseline, Weeks 4, 8, 12, 12/ET)	X	X		Placebo, 100mg, 150mg, Reference	Logistic regression
3.4	Percentage of subjects achieving DAS28 score <=3.2 at each visit (Baseline, Weeks 4, 8, 12, 16, 20, 24, 28, 32, 36, 40, 44, 48, 52, EOT)	X	X		100mg, 150mg, Reference	No statistical test
4.1	Percentage of subjects achieving "Good Response" using DAS28 EULAR response criterion at each visit (Baseline, Weeks 4, 8, 12, 12/ET)	X	X		Placebo, 100mg, 150mg, Reference	Logistic regression

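### The separation rule removes only covariates, so it cannot rescue a secondary or regional logistic model in which the placebo arm has no responders

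*SAP*

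**What the plan says.** SAP section 7.4.1.1 fits a maximum-likelihood logistic model with treatment, prior biologic-DMARD-IR, concomitant DMARD use at baseline and study region. The test is Wald: "The null hypotheses at Step 1 will be tested by Wald test at a two-sided significance level of 0.05". Each comparison has two arms: "For each comparison, only the data for two treatment groups to be compared will be used".

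The separation rule names its trigger and three covariates: "Only if quasi-complete separation, or complete separation occurs in the logistic model, then the study region, the prior biologic-DMARD-IR, and concomitant DMARD at Baseline". The remedy is that these three terms "will be removed from the logistic regression model, one by one, sequentially". Treatment is not on that list. The section does not say what follows if separation remains once all three covariates are gone.

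SAP section 7.4.2 carries the model to the secondary categorical endpoints, which "will be analyzed using logistic regression model, as described for the primary efficacy variable" unless Appendix 2 says otherwise. In Appendix 2, Table 19 assigns logistic regression to "Percentage of subjects achieving ACR20/50/70 at each visit (Weeks 4, 8, 12") and to DAS28 <2.6, SDAI ≤3.3, CDAI ≤2.8 and ACR/EULAR remission through Week 12/ET. Row 1.1.1.2 repeats ACR20/50/70 by study region. SAP section 4 plans 10 subjects per treatment group in Korea and the same in Taiwan.

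Fisher's exact test appears only for withdrawal due to lack of efficacy (section 7.2.1). Sections 7.4.1.6 and 7.4.2 add stratified log-rank tests of time to first response for several of the same endpoints.

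**The concern.** Removing covariates cures separation that a covariate causes, such as a small region with no responders in either arm. It does nothing when the empty cell belongs to the placebo arm. In that case the maximum-likelihood treatment coefficient is infinite whatever else is in the model. The software reports a large estimate with a much larger standard error, and the Wald p-value approaches 1 as iteration continues.

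An analyst who follows the rule to its end has therefore dropped three prespecified covariates and still has no usable odds ratio, interval or p-value. Any rescue would have to be improvised after seeing the data. Where a covariate is the cause, the rule works, but the covariate set then differs between endpoints and visits.

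**Working it through.** **Inputs from the documents.** 100 per arm for placebo and each dose; 10 per arm in Korea and in Taiwan; ACR20 planning rates of 25% (placebo), 54.5% (100 mg) and 65.5% (150 mg); two-sided 0.05 (SAP section 4). Phase IIb placebo ACR20 rate: 10.7% (protocol section 1.2.4). Placebo rates for ACR70, low-score and remission endpoints are not given, so those below are assumptions shown as a range.

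**The plan's own figure.** SAP section 4 states that "62 subjects per group will provide 90% power to detect a difference assumed in the Step 2 in the closed testing procedure". With p1 = 0.25, p2 = 0.545, d = 0.295 and mean 0.3975:

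- n = [1.960·√(2·0.3975·0.6025) + 1.2816·√(0.25·0.75 + 0.545·0.455)]² / 0.295² = 55.7
- with continuity correction: (n/4)·[1 + √(1 + 4/(n·d))]² = 62.3

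The stated 62 is reproduced to within rounding. It is not in dispute.

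**Step 1: does removing covariates help?** Logistic models were fitted by Newton iteration, stopped at 15 steps, to constructed data (100 versus 100, regions split 80/10/10, assumed covariate splits). Placebo had 0 responders and active 5 to 30. The treatment estimate was 13 to 15 with a standard error of 308 to 330. Wald p was 0.96 to 0.97 in the full model and after every removal, down to treatment alone.

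**Step 2: what does the Wald p-value measure?** Treatment-only model:

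| Placebo vs active | Wald p, stopped at 8 / 12 / 15 / 20 steps | Fisher | Firth penalised LR |
|---|---|---|---|
| 0/100 vs 8/100 | 0.50 / 0.88 / 0.97 / 0.996 | 0.0068 | 0.0028 |
| 0/100 vs 10/100 | 0.48 / 0.88 / 0.97 / 0.996 | 0.0015 | 0.0006 (OR 23) |
| 0/100 vs 20/100 | 0.43 / 0.87 / 0.96 / 0.996 | 6.6e-7 | 2.5e-7 (OR 51) |

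The Wald value follows the stopping point. One placebo responder is enough to restore it: 1/100 versus 10/100 gives Wald p = 0.024, and 1/100 versus 20/100 gives 0.002.

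**Step 3: how likely is an empty placebo arm?** P(no responders) = (1 − p)^n.

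- Primary ACR20, n = 100: 0.75^100 = 3e-13; at the phase IIb rate, 0.893^100 = 1.2e-5.
- Stringent endpoints, n = 100, assumed p = 0.5%, 1%, 2%, 3%, 5%: 61%, 37%, 13%, 5%, 0.6%.
- One region, n = 10, ACR20: 0.75^10 = 5.6%; 0.893^10 = 32%.
- At least one of the two small regions: 1 − (1 − 0.056)² = 11%; 1 − (1 − 0.322)² = 54%.

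An ACR70 responder is also an ACR20 responder, so the regional risk for ACR70 is at least as high.

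**Step 4: what does it cost?** Exact binomial power of the unadjusted two-arm test, 100 per arm, assumed rates, zero placebo cell counted as not significant:

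| Placebo vs active | Wald | Fisher |
|---|---|---|
| 1% vs 10% | 45% | 77% |
| 1% vs 15% | 62% | 97% |
| 2% vs 15% | 80% | 92% |
| 5% vs 20% | 90% | 88% |

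Part of the gap at low rates comes from the Wald test also being weak with one placebo responder (1 vs 10: 0.024 against Fisher 0.0097). By a 5% placebo rate there is no loss.

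**The case against.** The best defence is that little of consequence is exposed. The confirmatory closed test is safe, and the secondary tests have no multiplicity control and support no confirmatory claim. Counts and percentages are reported, so 0/100 versus 10/100 would be visible. The stratified log-rank tests tolerate an arm with no events and cover ACR20/50/70, DAS28-CRP <2.6, SDAI, CDAI and ACR/EULAR remission. The removal rule also works where a small region is the cause, since region goes first and the other two covariates stay. All of this stands, and it limits the severity. It does not close the gap: a log-rank test of time to first response is not a test of response at a visit, it gives no odds ratio, and the DAS28-ESR versions have no such test.

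A reader might infer more than the documents support:

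- **That the Wald test fails on the stringent endpoints generally.** It fails only with exactly zero placebo responders, at rates the documents do not give.
- **That it fails where the effect is largest.** That holds only on the odds-ratio scale. A 0 versus 10 result is a 10-point difference, against planned ACR20 differences of 29.5 and 40.5 points.
- **That the section 7.4.1.4 subgroup p-values are lost.** That section plans no testing; only the odds ratio and interval are affected.
- **That the re-randomisation test needs the same change.** Section 7.4.1.2 defines its statistic as the maximum-likelihood estimate over its standard error. Using Firth only in separated runs would mix two statistics in one reference distribution, for an endpoint where separation on treatment is negligible.

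**Conclusion.** The point holds, and it is minor. As written, the rule cannot cure separation on treatment, and following it to the end yields an odds ratio and Wald p-value with no information. The primary analysis is unaffected. For the full-size secondary comparisons, the risk is material only if the true placebo rate is about 3% or lower; that is an assumption, not a figure from the plan. For the Korean and Taiwanese analyses the risk follows from the documents' own numbers: 5.6% to 32% per region for ACR20, and no lower for ACR70. Log-rank tests remain valid for several of the affected endpoints.

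**What to change.** For the secondary and regional logistic models, replace the removal rule with this: if complete or quasi-complete separation occurs, keep all covariates and refit with Firth penalised likelihood, reporting profile penalised-likelihood confidence intervals and, where a test is planned, the penalised likelihood-ratio p-value. In the section 7.4.1.4 subgroups the refit supplies only the odds ratio and interval. Leave the re-randomisation statistic in section 7.4.1.2 as it is.

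The cost is one SAP sentence and one program option, settled before unblinding. The downsides are slightly shrunken estimates and a different estimator in separated tables, which a table footnote should state. An exact or score test would also give a usable unadjusted p-value (0 versus 10: Fisher 0.0015, score 0.0012). Firth is preferred here because it keeps the covariates and yields an odds ratio with an interval.
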